Objective measures to guide resuscitation became mainstream with the introduction of the pulmonary artery catheter in 1970 [11]. Over the ensuing decades, several randomized control trials demonstrated that the use of pulmonary artery catheters did not incur a survival advantage. In fact, the complexity inherent in placing, operating, and interpreting data from this tool is not without risk. Thus, in large part, these invasive devices have fallen out of favor [12-14]. There has since been a focus on developing minimally invasive and non-invasive tools to gauge intravascular volume status in order to accurately direct resuscitation.

Several of these techniques rely on cardiopulmonary interactions with the cyclic variations of intra-thoracic pressure produced by ventilation. In a mechanically ventilated patient, changes in intra-thoracic pressures are transmitted to the right ventricle with increased pressure during inspiration and decreased pressure during exhalation. In patients who are intravascularly deplete, these pressure shifts lead to larger variations in measured parameters such as pulse pressure, IVC collapsibility, and plethysmography throughout the respiratory cycle. **Figure 2** describes the variation in pulse pressure which is represented by ΔPs . Plethysmography variation and CI are derived in a similar fashion using corresponding waveforms with the notion that more variation correlates with less intravascular volume.

Figure 2

Pp_{min} , minimal arterial pulse pressure; Pp_{max} , maximal arterial pulse pressure; Ps_{min} , minimal arterial systolic pressure; Ps_{max} , maximal arterial systolic pressure; ΔPs , pulse pressure variability. From Vasodilation increases pulse pressure variation, mimicking hypovolemic status in rabbits. Westphal GA, Goncalves AR, Bedin A et al., 2018, *Clinics*[15].

Tools and indices available to measure intravascular volume status are numerous with the most frequent utilized ones described in **Table 2**. These indices range from simply measuring the systolic blood pressure to using computer generated algorithms in order to calculate a CRI. This armamentarium has vast applicability, but the predictive utility is variable, influenced by several confounders, and must be applied in the appropriate clinical setting.

Table 2: Intravascular Volume Status Measurements

INVASIVE DEVICES	
SWAN-GANZ CATHETER	CO, SVR, SV, LVEDAI, GEDVI, CVP, PCWP
CENTRAL VENOUS CATHETERS	CVP, SvO_2 , ΔpCO_2
ARTERIAL LINES	PPV, SVV, SPV
ESOPHAGEAL DOPPLER	ΔVpeak , SV, CO, ABF
CAPNOMETER	ΔETCO_2
NON-INVASIVE	
VITAL SIGNS	HR, SBP
PLETHYSMOGRAPHY	Plethysmography variation index
ULTRASONOGRAPHY	IVC CI
ECHOCARDIOGRAM	CO, SV
COMPENSATORY RESERVE INDEX	CRI

CO – cardiac output, SVR – systemic vascular resistance, SV – stroke volume, LV – left ventricular end-diastolic area index, GEDVI – global end-diastolic volume increase, CVP – central venous pressure, PCWP – pulmonary capillary wedge pressure, SvO_2 – mixed venous oxygen saturation, ΔpCO_2 – delta partial pressure of carbon dioxide, PPV – pulse pressure variation, SVV – stroke volume variation, SPV – systolic pressure variation, ΔVpeak – delta aortic blood flow peak velocity, ABF – aortic blood flow, ΔETCO_2 – delta end-tidal carbon dioxide level, HR – heart rate, SBP – systolic blood pressure, IVC – inferior vena cava, CI – collapsibility index, CO – cardiac, CRI – compensatory reserve index

While large series have evaluated the predictive utility of various devices in adults, reports appraising tools used to assess fluid responsiveness in children are limited with heterogeneous findings [16]. A systematic review by Gan et al. published in 2013 reviewed 12 pediatric studies that, in total, evaluated 24 markers of fluid responsiveness in 439 children. The only variable that was repeatedly found predictive of fluid responsiveness and distinguish fluid responders from non-responders was variation in aortic blood flow peak velocity (ΔVPeak) obtained from the CardioQ-EDM. Not only has this tool been shown to predict those who will benefit from additional fluid, but, based on changes in pre- and post- fluid ΔVPeak , in it has been shown to accurately distinguish fluid responders from non-responders [7].

[figure not shown]
In adults, the esophageal CardioQ-EDM has been used both in the operating room and ICU. Among adult trauma patients admitted to the ICU, CardioQ-EDM has been used to guide resuscitation and shown to decrease infection complications as well as reduce ICU and hospital length of stay [17]. In children, increased enthusiasm in recent years has led to a number of small clinical trials most of which have been performed in Europe. In a metanalysis published in 2016 included six studies and 163 ventilated children, comparing CardioQ-EDM to echocardiography the authors concluded that the area under the summary receiver operating characteristic curve to distinguish responders from

non-responders for Δ VPeak was 0.94 [18]. While the optimal Δ VPeak varied from 7-20% among studies, one of the larger series using a Δ VPeak of 10% as a threshold found the sensitivity and specificity to be 100% in distinguishing fluid responders based on aortic velocity-time integrals identified by transthoracic echocardiogram [7]. Based on these results, we plan to define fluid responders as those who have $>10\%$ Δ VPeak between pre- and post-fluid challenge.

Bedside evaluation of the IVC to calculate the CI is a commonly used tool in adults [19, 20]. It serves as a surrogate to measure preload variation induced by mechanical ventilation. The technique requires limited ultrasonographic experience often at the critical care or anesthesia fellow level. In pediatrics, the predictive utility of IVC CI has only been evaluated in small series with conflicting results [21].

The CRI is another non-invasive devise using a photoplethysmographic probe (CipherOx-CRI) placed on the index finger. Based on data gathered from the probe, a computer-generated algorithm is then used to calculate a number between zero and one, referred to the CRI (Figure 3) [22]. The CRI correlates to one's intravascular volume status and proximity to hemodynamic collapse [23].

Figure 3

Legend: CRI, compensatory reserve index. CRI=1 is normovolemia and CRI=0 is the point at which the patient is at highest risk for hemodynamic decompensation.

Confounding factors that can influence dynamic measurements must also be considered. For instance, cardiac arrhythmias, small tidal volumes, spontaneous respiration, and high positive end-expiratory pressure have been found to decrease the predictive utility of pulse pressure variability and IVC CI [24-26]. Thus, it is paramount to use and apply these measurements in the appropriate clinical setting. Presumably, the influence confounding variables have on the predictive utility of these indices in children is similar to that of adults, however, comparative analyses have not been performed. Thus, when interpreted in the appropriate clinical context, these minimally and non-invasive devices are tools available to guide a balanced fluid resuscitation; however, while small series exist in various pediatric populations, validation is necessary in order to apply these tools in hypovolemic children with significant blood loss.

Protocol #: 18-2513

PI: [name]

Version date: 07/01/2019

While numerous tools are available to guide resuscitation, one potential benefit of this project is to validate the use of CipherOx-CRI in this cohort. If CRI proves to be a valuable predictor of intravascular volume status and the need for volume expansion, this could negate the need for arterial line placement which is time consuming, invasive, and associated with complications such as arterial thrombosis. Furthermore, after validation in this cohort, additional studies could be performed in other groups of children at risk for hemorrhagic shock in the hopes to guide ongoing resuscitation accurately without the need for invasive devices.

3. Specific Aims and Hypotheses:

Aim I: Among infants undergoing cranial vault reconstruction for craniosynostosis, we aim to determine the proportion who respond to clinically administered fluid or blood products defined by pre- and post-fluid challenge $\Delta V_{Peak} > 10\%$.

Hypothesis Ia: We hypothesize that approximately half of the cohort will be fluid responsive defined by ΔV_{Peak} by $> 10\%$ after a 10 mL/kg fluid bolus is administered immediately following induction. Although this is a prediction, it is based on previous published reports suggesting a relatively even distribution among patients who clinicians believe need volume expansion. Additionally, because these children have a mean weight of 6.4 kg and will have been nil per os for several hours prior to surgery, they are at risk for intravascular volume depletion even prior to blood loss.

Hypothesis Ib: Because clinicians use pulse pressure variability, heart rate, systolic blood pressure, urine output, and blood loss to gauge need for ongoing resuscitation (either crystalloid, colloid, or blood), we suspect that more than half of subsequent fluid challenges will be given to infants who are fluid responsive (defined by a pre- and post-bolus ΔV_{Peak} of $> 10\%$).

Aim II: To determine the PPV, NPV, sensitivity, specificity, and optimal threshold for CRI, collapsibility index, pulse pressure variability, stroke volume variability, heart rate, systolic blood pressure, and mean arterial pressure as tools to predict fluid responsiveness using pre- and post-fluid challenge $\Delta V_{Peak} > 10\%$ to define fluid responders.

Hypothesis II: CRI and collapsibility index will reliably predict fluid responsive patients with an approximate area under the receiver operating characteristic curve (AUROC) of 0.9 while other indices will have a lower predictive accuracy.

Aim III: Evaluate confounding variables that may influence predictive measures outlined in Aim II.

Hypothesis III: Confounding variables that may decrease the predictive accuracy of indices described in Aim II include spontaneous breathing over the ventilator, minimal blood loss, and hypothermia

4. Materials and Methods:

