A plethora of indices and tools have been studied and marketed to assess intravascular volume status with only a few proven reliable with reproducible results. Based on pre-fluid challenge values, several of these tools have been used to predict who may benefit from additional fluid (fluid responders). Alternatively, some of these tools have been used to distinguish fluid responders from non-responders based on changes in pre- and post-fluid challenge values. Among these tools, the pulmonary artery catheter provides measurements of both left and right heart pressures which can be applied to calculate the cardiac output (CO) and stroke volume (SV). Changes in these values (e.g. an increase in the stroke volume by 10%) between pre- and post-fluid challenge have been used to define fluid responders. This devise, however, is invasive with several significant risks, and therefore is rarely used in children. Echocardiography, on the other hand, is a non-invasive bedside study also used to assess CO and SV but is expensive and requires trained echosonographers for application. Further, because a transthoracic probe is required to obtain the images, application in the operating room is difficult as the chest is often in the operating field limiting access to the echosonographer. Lastly, the esophageal aortic blood flow device (CardioQ-EDM, Deltex Medical, Chichester, UK) has been found in multiple adult and pediatric studies to reliably distinguish fluid responders from non-responders intensive care unit (ICU) and operating room [2-6]. Much like an orogastric tube, this device is simply placed by a provider in the patient's esophagus and uses Doppler waveforms to measure aortic blood flow velocities (**Figure 1**). Variations in the amplitude of peak velocities has been shown to corelate with intravascular volume status[2-6]. Specifically, a change in the peak velocity by greater than 10% between pre- and post-fluid challenge values has

Protocol #: 18-2513

[figure not shown]
PI: [name]

Version date: 07/01/2019

[figure not shown]
been shown to accurately distinguish those who are fluid responsive from those who are not with similar accuracy to echocardiography and pulmonary artery catheter readings[7].

Figure 1

A

B

Legend: A) Illustration of CardioQ-EDM position. In children age 15 years and younger, the device is introduced through the oral cavity. B) Correct placement confirmed by descending aortic waveform.

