4.4 Definitions

- *Bolus* – 10 - 20 ml/kg fluid (isotonic crystalloid, colloid, or blood product) up to 1 L and given within a 10 minutes period
- *Fluid responders* – Children who have a pre- and post-fluid challenge $\Delta VPeak > 10\%$ calculated using the equation ($\Delta VPeak_{pre} = (VPeakmax_{pre} - VPeakmin_{pre}) /$

Protocol #: 18-2513

PI: [name]

Version date: 07/01/2019

$$[(V_{peakmean_{pre}})] - (\Delta V_{Peak_{post}} = (V_{Peakmax_{post}} - V_{Peakmin_{post}}) / [(V_{peakmean_{post}})] \times 100$$

- *Multiple fluid challenges* – If more than one fluid bolus is administered at least 30 minutes apart, they will be reported as individual events
- *Pre-bolus measurements* – Hemodynamic measurements will be calculated or recorded three times thirty seconds apart and averaged just before a bolus is administered. Cine loops from IVC measurements will be recorded three times, thirty seconds apart for post-hoc CI calculation. Peak aortic velocity and CRI will be recorded on the EDM monitor and averaged over 90 seconds.
- *Post-bolus measurements* - Hemodynamic measurements will be calculated or recorded three times and averaged five minutes after a bolus is completed. These measurements will be time and repeated in an identical fashion to pre-bolus measurements.

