2. After positioning the patient for surgery, the CardioQ-EDM device will be placed through the mouth into the esophagus by the PI or Co-investigators (Drs. [name] or [name]) and the aortic Doppler waveform will be confirmed. Additionally, the CipherOx-CRI finger probe will be placed, and a baseline IVC CI will be measured and recorded.
3. Baseline values and measurements (included in **Table 3**) will be recorded. Additionally, the baseline ΔV_{Peak} and CRI will be recorded.
4. A protocolized 10 mg/kg crystalloid fluid bolus will be administered
5. Two minutes after the bolus has completed, repeat EDM and CRI values will be recordings and a repeat abdominal ultrasound to measure the IVC CI will be obtained.
6. If an additional fluid bolus or blood transfusion is administered during the remainder of the procedure, steps 3 and 5 will be repeated.

4.6.1 Demographic Data: Age, weight, height, body mass index (BMI), gender, and ethnicity will be collected from medical records.

4.6.2 Ventilator Data: pressure or volume control, tidal volume (ml/kg) and peak end-expiratory pressure (PEEP), peak inspiratory pressure (PIP), and spontaneously breathing.

4.6.3 CardioQ-EDM Data: Based on a validated internal nomogram derived from the child's age, height, and weight[27], peak velocities will be obtained from the Cardio-EDM monitor.

4.6.4 Fluid Data/Vasopressor Administration: Number, time, type, and volume of fluid/blood administered will be recorded in real time. Vasopressor agent, dose, and time administered will also be reported.

4.6.5 Waveform/Vital Data: As it is currently not possible to extract waveform data from the operating room monitors, we will record data in real time. Values listed below will be reported on an excel spreadsheet.

Parameters to measure:

All parameters will be measured x 3 with 30 seconds between each measurement and averaged

- Systolic blood pressure (measured by arterial line)
- Mean arterial pressure (calculated from arterial line)
- Heart rate
- Pulse pressure variability (measured by arterial line) = acquired from arterial line
- Stroke volume variability – acquired from arterial line
- $\Delta V_{peak} = (V_{Peakmax} - V_{Peakmin}) / [(V_{peakmean}] \times 100$
- Compensatory reserve index – algorithmically generated
- Inferior vena cava collapsibility index = Maximum diameter (expiration) – minimum diameter (inspiration)/maximum diameter (expiration) in M mode

4.7 Data Blinding:

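### The responder label is itself a respiratory-variation index, so its errors may be shared with PPV, SVV and IVC CI and bias their ranking against other indices

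*Combined protocol and SAP*

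**What the plan says.** Section 4.6.5 computes ΔVPeak as "V_{Peakmax} - V_{Peakmin}) / [(V_{peakmean", times 100. The definition of responders in 4.4 ("Children who have a pre- and post-fluid challenge" ΔVPeak above 10%) subtracts the post-bolus value of this index from the pre-bolus value. The background supports the choice by saying that "Variations in the amplitude of peak velocities has been shown to corelate with intravascular volume status". The label is thus a fall in within-breath variation, not a rise in flow.

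On mechanism, the background says "Several of these techniques rely on cardiopulmonary interactions with the cyclic variations of intra-thoracic pressure produced by ventilation" and names pulse pressure, IVC collapsibility and plethysmography as examples. It later describes CI as a surrogate for preload variation caused by ventilation. It also warns that "small tidal volumes, spontaneous respiration, and high positive end-expiratory pressure have been found to decrease the predictive utility"; the sentence goes on to name pulse pressure variability and IVC CI, and no other index.

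Hypothesis III (section 3) predicts that spontaneous breathing lowers the accuracy of the Aim II indices. Section 4.6.2 and the Aim III table in section 5 collect spontaneous breaths, tidal volume and PEEP, and the Aim III table adds paralysis. The visible text does not fix ventilation, require paralysis or exclude boluses given during spontaneous breathing.

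Table 2 lists "ΔVpeak , SV, CO, ABF" as outputs of the esophageal Doppler. Section 4.6.3 says only that "peak velocities will be obtained from the Cardio-EDM monitor". No second reference is planned in the visible text.

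**The concern.** Comparing AUROCs against an imperfect reference is fair only if the reference's errors are equally unrelated to every index. Here three of the seven indices in Mock-up Table 2 (PPV, SVV, CI) belong to the reference's own family: PPV and CI by the mechanism the protocol gives, SVV by its name. A child whose swings are large because of the ventilator settings rather than volume depletion could have a high PPV, a high CI and a high starting ΔVPeak with more room to fall. The index and the label would then agree for a reason unrelated to fluid responsiveness. Heart rate, SBP and MAP get no such help.

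Two conclusions are exposed. Hypothesis II ranks CRI and CI, at about 0.9, above the other indices, and the protocol hopes to use such results to replace arterial lines. Hypothesis III asks whether spontaneous breathing degrades the indices, but a change in measured accuracy could come from the label.

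**Working it through.** The plan states no figure on this point, so there is none to reproduce. The check asks which way shared error pushes the results and how far.

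**1. Inputs.** From the documents: about half the children are responders (Hypothesis Ia); the summary AUROC for ΔVPeak against echocardiography is 0.94; the label requires a drop above 10. Assumed: the error sizes, the error correlation ρ, and that 0.94 is a fair stand-in for the accuracy of the pre-minus-post label.

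**2. Shared-error model.** Let true response D ~ N(0,1), with a true responder having D > 0. The reference is R = D + 0.5·e_R and the label is R > 0. An index is X = D + s·e_X with corr(e_R, e_X) = ρ. The reference then has AUROC 0.94 against truth. The label agrees with truth in 1 − arccos(1/√(1 + 0.5²))/π = 1 − 0.464/3.142 = 0.85 of cases. Simulated AUROCs (1,000,000 draws):

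| Index error s | True AUROC | Observed, ρ = 0 | Observed, ρ = 0.3 | Observed, ρ = 0.6 |
|---|---|---|---|---|
| 0.75 | 0.88 | 0.838 | 0.880 | 0.925 |
| 1.0 | 0.83 | 0.794 | 0.844 | 0.894 |

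The gaps between two equally good indices, one sharing the reference's error and one not, are:

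- s = 0.75: 0.880 − 0.838 = 0.04 and 0.925 − 0.838 = 0.09.
- s = 1.0: 0.844 − 0.794 = 0.05 and 0.894 − 0.794 = 0.10.

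Part of each gap is the independent index being marked down by label error. At ρ = 0.6 the sharing index is also marked up, from 0.88 to 0.93, which would carry it past the 0.9 of Hypothesis II.

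**3. Spontaneous breathing.** A second model uses the label's own structure: pre-bolus minus post-bolus variation above 10 points. All of its settings are assumed. Mean pre-bolus variation is 20 in responders and 10 in non-responders (SD 4), and the mean drops are 13 and 4 (SD 3). A ventilatory gain (log-SD 0.2) multiplies ΔVPeak and PPV, and each index carries noise of SD 5. Three forms of disturbance were compared (values without → with spontaneous breaths):

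| Disturbance | Label sens. / spec. | PPV true AUROC | PPV observed | Observed, index with no ventilatory term |
|---|---|---|---|---|
| Changes the gain | 0.77 / 0.97 → 0.65 / 0.91 | 0.84 → 0.76 | 0.83 → 0.88 | 0.80 → 0.73 |
| Added swing, independent pre and post | 0.77 / 0.98 → 0.65 / 0.81 | 0.84 → 0.80 | 0.83 → 0.80 | 0.80 → 0.68 |
| Added swing, same pre and post | 0.77 / 0.98, unchanged | 0.84 → 0.80 | 0.83 → 0.79 | 0.80, unchanged |

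The true AUROC of the index with no ventilatory term is about 0.86 to 0.87 throughout. Under a gain change, PPV truly worsens but appears to improve, and the unaffected index appears to worsen. Under a constant added swing the subtraction removes the disturbance and the comparison is sound.

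**The case against.** The strongest reply is that ΔVPeak has cited paediatric support: AUROC 0.94 across six studies and 163 ventilated children, and sensitivity and specificity of 100% in one series at the 10% threshold. A near-perfect reference has little error to share. This limits the size but does not remove the problem. The gaps above already assume 0.94, and the cited optimal cut-offs range from 7 to 20%. In that evidence ΔVPeak was the index test, assessed against echocardiography; here it becomes the reference standard. The pooled studies were in ventilated children and are not shown to cover spontaneous breathing over the ventilator.

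Three stronger readings are tempting, and the documents do not support them.

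- *The label is biased against CRI.* This needs CRI to be free of ventilatory error. The protocol says only that CRI is an algorithm applied to photoplethysmographic data, and it lists plethysmography among the measures that vary with respiration. Heart rate, SBP and MAP are the clearer disadvantaged comparators. Any bias against CRI would also tend to miss a useful device rather than endorse a poor one.
- *Hypothesis III cannot be interpreted.* Distortion of ΔVPeak by spontaneous breathing is an inference from mechanism, since the protocol's warning names only PPV and IVC CI. A constant disturbance cancels.
- *The spurious gap reaches 0.15.* That follows only if the reference is given as much error as the indices, which puts its own AUROC at 0.83 to 0.88, below the cited 0.94.

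It is also fair to object to replacing the label. The stroke-volume criterion in the background ("an increase in the stroke volume by 10" percent) is given for the pulmonary artery catheter, not for this probe.

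**Conclusion.** The concern holds as a threat of correlated error, not as a demonstrated bias. By its formula the reference is a respiratory-variation index of the same family as PPV, SVV and CI, and the visible plan has no reference outside that family. If errors are shared, the direction is clear: the sharing indices look better relative to those that do not share. The size cannot be derived from the documents. About 0.04 to 0.10 in AUROC rests on assumed correlations of 0.3 to 0.6, true AUROCs of 0.83 to 0.88, and a reference near 0.94. The gap vanishes if the reference is error-free or the errors are uncorrelated. Whether CRI is among the disadvantaged indices is open. The spontaneous-breathing part of Hypothesis III may be misread if the disturbance scales the swing or changes between readings, but not if it is constant. A sensitivity analysis is the proportionate response.

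**What to change.** - **4.6.3:** record Doppler stroke volume (or aortic blood flow) at every pre- and post-bolus reading, alongside peak velocities.
- **4.8:** keep ΔVPeak as the primary label. Add a sensitivity analysis that repeats the Aim II AUROCs and the Aim III spontaneous-breathing analysis with response defined as a stroke-volume rise of more than 10%.
- **4.8:** repeat Aim II in boluses without spontaneous breaths. Section 4.6.2 already collects this; state that it is noted for each bolus.
- **Reporting:** describe any ranking of indices that changes between labels as dependent on the reference.
- **Background and 4.4:** reconcile the wording. The background also states the criterion as a change in peak velocity itself, which would not be a variation index.

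The cost is one more value per reading from a monitor already in use, and a second set of results. The value should be written down at the time, because 4.6.5 says waveforms cannot be extracted from the operating-room monitors. The downsides are that the two labels may disagree, and that the visible text cites no paediatric validation of Doppler stroke-volume change. The stroke-volume label therefore belongs in a sensitivity analysis.

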4.8 Data Analysis

Protocol #: 18-2513

PI: [name]

Version date: 07/01/2019

Univariate comparisons between various measures will be compared between the fluid responder and non-responder groups using t-tests or Fisher's exact test for continuous and categorical measures, respectively. Area under the curve will be calculated for CI and CRI using both simple logistic regression models including no confounders and multiple logistic regression models including confounders. Confounders will be identified for inclusion in the multiple logistic regression models by calculating the univariate association with the gold standard (using a $p < 0.10$ threshold). These adjusted models will be used to verify thresholds for classification using CI and CRI which will then be applied to calculate classification summary measures (e.g., PPV, NPV, sensitivity, and specificity). Data analysis will be performed by a biostatistician funded by the Division of Pediatric Surgery using R and SAS statistical software programs.

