4.9.2 CardioQ-EDM Contraindications

- Doppler probes (DP240 and I2n) should not be placed in patients under 16 years of age. We will be using the KDP72 probe
- Do not use where nasal injuries are apparent or may have occurred.
- Do not use where nasal polyps exist.
- Do not use where there are circumstances of facial trauma.
- Do not use where there is a risk of brain injury.
- Do not use in patients undergoing intra-aortic balloon pumping.
- Do not use with carcinoma of the pharynx, larynx or esophagus.
- Do not use with aneurysms of the thoracic aorta.
- Do not use with tissue necrosis of the esophagus or nasal passage.
- Do not use in close proximity to laser surgery.
- Do not use in patients with pharyngo-oesophago-gastric pathology and/or severe bleeding diatheses.

5. Specific Aims:

Aim I: Define fluid responders based on aortic ΔV_{peak} : Among infants undergoing cranial vault reconstruction for craniosynostosis, we aim to determine the proportion who respond to clinically administered fluid or blood products defined by pre- and post-fluid challenge EDM $\Delta V_{Peak} >10\%$.

Mock-up Table 1: Demographics of Responders and Non-Responders to Initial 10 mL/kg bolus prior to surgical incision

Variable	Responders	Non-Responders	P-value
Demographics			
Age			
Weight			
Height			
BMI			
Gender			
Ethnicity			
Duration of NPO status			
Associated syndrome			

Legend: BMI, body mass index; npo, nil per os

Aim II: Calculate the PPV, NPV, sensitivity, specificity, and optimal threshold for CRI and collapsibility index as tools to prediction fluid responder

Protocol #: 18-2513

PI: [name]

[figure not shown]
Version date: 07/01/2019

		Fluid Responsive	
		Yes	No
CRI Threshold	+	True Positive	False Positive
	-	False Negative	True Negative

		Fluid Responsive	
		Yes	No
CI Threshold ($\geq 15\%$)	+	True Positive	False Positive
	-	False Negative	True Negative

Performance will also be calculated for heart rate, systolic blood pressure, mean arterial pressure, pulse pressure variability and stroke volume variability. Two separate analyses will be performed – one for the 10 ml/kg protocolized bolus provided immediately after induction and one accounting for all boluses provided.

Mock-up Figure

Mock-up Table 2 – Performance at predicting fluid responsiveness

Variable	Correlation (r)	AUC
IVC CI		
CRI		
SBP		
PPV		
SVV		
MAP		
HR		

Protocol #: 18-2513

PI: [name]

Version date: 07/01/2019

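### Where a cut-off is taken from the trial data, sensitivity, specificity and predictive values are scored on the same children with no correction, so they will be too high on average

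*Combined protocol and SAP*

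**What the plan says.** Section 3, Aim II, is "To determine the PPV, NPV, sensitivity, specificity, and optimal threshold for CRI, collapsibility index, pulse pressure variability, stroke volume variability". The list then adds three vital signs (mean arterial and systolic pressure, and heart rate), which makes seven indices. Fluid responsiveness by the esophageal Doppler is the reference, and the cohort is a single arm.

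Section 4.8 gives the method for two of the seven: "Area under the curve will be calculated for CI and CRI using both simple logistic regression models including no confounders", and also with confounders. It continues: "These adjusted models will be used to verify thresholds for classification using CI and CRI which will then be applied to calculate classification summary measures".

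Section 5, Aim II, prints a CI threshold of 15% or more in its mock two-by-two table. The CRI table carries no value, and none is given for the other five indices. Section 5 also plans a first-bolus analysis and an all-bolus analysis, both from the same children.

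On direction, the Figure 3 legend says "CRI=1 is normovolemia and CRI=0 is the point at which the patient is at highest risk for hemodynamic decompensation". The Background says of the respiratory-variation measures that "more variation correlates with less intravascular volume".

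On the status of the result, the paragraph before section 3 says "one potential benefit of this project is to validate the use of CipherOx-CRI in this cohort". It sends later studies to other pediatric groups at risk of hemorrhagic shock.

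**The concern.** A cut-off searched for in a data set fits the chance features of that data set. Accuracy computed at that cut-off in the same children is apparent accuracy, and on average it exceeds what the cut-off would achieve in new children. This happens with a single index and no covariates, so it is separate from the question of which confounders enter the model.

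The text available names no split sample, cross-validation, bootstrap or external sample. The two bolus analyses cannot test each other, because they share children.

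The Background hopes to replace arterial lines if CRI or CI predicts as well as current indices. A bedside decision of that kind would use a threshold and its error rates, which are the figures affected. No retest of the threshold in this population is described.

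**Working it through.** **No figure to reproduce.** The text available gives no sample size, precision target or expected sensitivity or specificity. The AUROC of about 0.9 for CRI and CI is a hypothesis.

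**Inputs**
- True AUC: 0.9 (Hypothesis II). The other indices are only said to be lower, so 0.5 to 0.8 was used for them.
- Proportion of responders: about one half (Hypothesis Ia).
- Number of children: assumed. Section 4.2 lists 30 probes and the Background gives 50 to 70 cases a year. Range used: 20 to 100.
- Criterion for an optimal threshold: not defined in the documents. Assumed to be maximum Youden, J = sensitivity + specificity − 1.
- Index: assumed binormal with equal variance, one bolus per child, direction fixed in advance.

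**Reference value.** The separation of the two groups is d = √2 × Φ⁻¹(AUC), and the best attainable value is J = 2Φ(d/2) − 1.
- AUC 0.9: d = 1.414 × 1.282 = 1.812, so J = 2 × 0.8175 − 1 = 0.635.
- AUC 0.7: d = 1.414 × 0.524 = 0.742, so J = 2 × 0.6446 − 1 = 0.289.

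**Simulation.** In each of 4,000 runs per setting, the maximum-J cut-off was found in the sample, scored there (apparent), and then scored against the true distributions (new children).

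| n | True AUC | J apparent | J new children | Difference |
|---|---|---|---|---|
| 20 | 0.9 | 0.760 | 0.588 | 0.172 |
| 30 | 0.9 | 0.734 | 0.600 | 0.134 |
| 60 | 0.9 | 0.702 | 0.611 | 0.091 |
| 100 | 0.9 | 0.685 | 0.618 | 0.067 |
| 30 | 0.8 | 0.570 | 0.411 | 0.159 |
| 30 | 0.7 | 0.433 | 0.254 | 0.179 |
| 30 | 0.5 | 0.205 | 0.000 | 0.205 |

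Repeat runs, including runs with exactly equal groups, agree to about 0.01; for example, apparent J is then 0.75 at n = 20.

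The four measures at n = 30, apparent to new children:

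| Measure | AUC 0.9 | AUC 0.7 |
|---|---|---|
| Sensitivity | 0.871 to 0.805 | 0.728 to 0.641 |
| Specificity | 0.863 to 0.794 | 0.705 to 0.613 |
| Positive predictive value | 0.870 to 0.810 | 0.737 to 0.644 |
| Negative predictive value | 0.875 to 0.816 | 0.746 to 0.652 |

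That is 6 to 7 points each at AUC 0.9 and about 9 points each at AUC 0.7.

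**What is not biased.** With a cut-off fixed before the data (n = 30, AUC 0.9), mean J is 0.637 against the attainable 0.635. With direction fixed, the mean AUC is 0.900 for a true 0.900.

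**Learning the direction as well (n = 30).** At AUC 0.9, J is 0.734 either way. At AUC 0.8 it is 0.574 against 0.570. For a useless index, J rises from 0.205 to 0.290 and the mean AUC from 0.50 to 0.58.

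**Does a bootstrap repair it?** With the cut-off re-selected in each resample (n = 30), J falls from 0.723 to 0.643 at AUC 0.9, where the true value is 0.597. The share removed is 0.080/0.126 = 63%. At AUC 0.7 it falls from 0.432 to 0.325 (true 0.257): 0.107/0.175 = 61%. Repeat checks gave 57% to 67%.

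**The case against.** The case for the plan has several sound parts, and they limit what a reader may infer.

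- **That all seven indices are affected.** CI has a printed cut-off, and scoring CI at that fixed value carries no selection bias. But section 3 still seeks an optimal CI threshold and section 4.8 still verifies one, so the documents do not settle whether it is fixed.
- **That the logistic fit lets a wrong-way index pass as predictive.** Logistic AUCs are stated only for CI and CRI, and the Background gives the expected direction for both. Mock-up Table 2 reports a correlation beside each AUC, so a reversed index should be visible. The effect is negligible at AUC 0.8 to 0.9. What remains is that section 4.8 does not bind the analysis to the stated directions, and none is given for heart rate, systolic or mean arterial pressure.
- **That the comparison of CRI and CI with the vital signs is distorted.** Hypothesis II compares AUROCs, and these are not inflated when direction is fixed. Only a comparison made on cut-off measures would be affected.
- **That the trial has at most 30 children.** This is a probe count, not a stated sample size, and the bias shrinks as n grows.
- **That calling the exercise validation is wrong.** The word is applied to CRI, which comes from an existing algorithm. Testing that algorithm's discrimination in a new population can fairly be called validation. A threshold found in the same data cannot.

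None of this answers the central point: a data-derived threshold is scored on its own derivation sample with no correction.

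**Conclusion.** The concern holds for CRI, pulse pressure variability, stroke volume variability, heart rate, systolic and mean arterial pressure wherever their cut-offs are taken from the trial data, and for CI if its threshold is re-derived. Sensitivity, specificity and both predictive values will then be too high on average. At true AUC 0.9, the overstatement of Youden's index runs from about 0.17 with 20 children to 0.07 with 100. At 30 children it is 0.13 for AUC 0.9 and 0.18 for AUC 0.7.

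These sizes rest on the assumed n, half responders, a binormal index, one bolus per child and a maximum-Youden cut-off. They are averages; a single data set may show more or less. Parts of the document were not in the text reviewed, so a sample size or validation step stated there cannot be excluded.

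The documents do not support extending the criticism to the index-only AUROC in a fixed direction, to CI held at 15%, or to the assessment of CRI's discrimination. This should be corrected before analysis; it does not call the design into question.

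**What to change.** In section 4.8:

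1. State one cut-off criterion for all indices. Report CI accuracy at the printed 15%, and reconcile section 3 (Aim II), section 4.8 and section 5 (Aim II) on whether that value is fixed or re-derived.
2. For each data-derived cut-off, report optimism-corrected sensitivity, specificity, positive and negative predictive value, with confidence intervals, beside the apparent values. Use a bootstrap that resamples children, not boluses, because the all-bolus analysis has repeated events per child, and that re-selects the cut-off in every resample. State that the correction is partial, removing roughly 60% of the bias in simulation.
3. Compute the empirical AUC in the direction the Background already gives for CRI and the respiratory-variation indices. Write that direction down for stroke volume variability too, which the Background passage does not name, and state one for heart rate, systolic and mean arterial pressure before analysis.
4. Describe the CRI threshold as derived and awaiting a test in new children. Validation may remain as the term for assessing the existing CRI algorithm's discrimination.

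The cost is a few lines of R and some rewording, with no added children or procedures. The one drawback is that the reported accuracy will be lower.
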